UMMC conducts surveillance biopsies at 3 and 12 months post-KTx on some adult transplant recipients, providing an ideal opportunity to assess kidney tissue for EBV and CMV via molecular and immunological assays. We think it likely that post-KTx, kidneys exposed to an immunosuppressed milieu allowing viral multiplication will increase the likelihood of isolating the virus from infected recipients; a pivotal step in our understanding of the mechanisms of CMV and EBV infection post-KTx.

In summary, valA is less expensive, with fewer adverse effects, and less likelihood of causing leucopenia than valG. If this agent has equivalent efficacy in CMV and any efficacy in EBV prophylaxis, the use of valA will result in significant financial savings, a reduced risk of leucopenia-associated infection, and a lower incidence of rejection by allowing the use of standard MMF doses.

1.2 *Investigational Agent*

Valacyclovir (valacyclovir hydrochloride) is the hydrochloride salt of the *L*-valyl ester of the antiviral drug acyclovir. Caplets are for oral administration. Each caplet contains valacyclovir hydrochloride equivalent to 500 mg or 1 gram valacyclovir and the inactive ingredients carnauba wax, colloidal silicon dioxide, crospovidone, FD&C Blue No. 2 Lake, hypromellose, magnesium stearate, microcrystalline cellulose, polyethylene glycol, polysorbate 80, povidone, and titanium dioxide. The blue, film-coated caplets are printed with edible white ink.

Valacyclovir oral suspension (25 mg/mL or 50 mg/mL) may be prepared extemporaneously from 500 mg VALTREX Caplets for use in pediatric patients for whom a solid dosage form is not appropriate.

The chemical name of valacyclovir hydrochloride is *L*-valine, 2[(2-amion-1,6-dihydro-6-oxo-9*H*-purin-9-yl)methoxy]ethyl ester, monohydrochloride.

Valacyclovir is a nucleoside analogue DNA polymerase inhibitor. Valacyclovir hydrochloride is rapidly converted to acyclovir which has demonstrated antiviral activity against HSV types 1 (HSV-1) and 2 (HSV-2) and VZV both in cell culture and *in vivo*. The inhibitory activity of acyclovir is highly selective due to its affinity for the enzyme thymidine kinase (TK) encoded by HSV and VZV. This viral enzyme converts acyclovir into acyclovir monophosphate, a nucleotide analogue. The monophosphate is further converted into diphosphate by cellular guanylate kinase and into triphosphate by a number of cellular enzymes.

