1.4 Dose Rationale and Risk/Benefits

Prior research at the University of Minnesota has shown that valacyclovir 1g every 8 hours for a total daily dose of 3g is well tolerated and was associated with a reduction in EBV excretion (1) in patients with infectious mononucleosis. Subsequently a study done at the University of Minnesota to characterize the pharmacokinetics and explore the pharmacodynamics of acyclovir in plasma and oral washings of 8 subjects with EBV infectious mononucleosis receiving the same daily dose of valacyclovir (3g) as a twice daily dosing of 1500 mg twice daily demonstrated safety and showed that the quantity of EBV DNA in oral washings and blood, and the severity of illness, measured by a graded scale, decreased during treatment (9).

Therefore in order to increase the likelihood of compliance in our patients, we have decided to utilize 1.5g twice a day dosing of valacyclovir and since it was shown to be effective as therapy in the above study, we hypothesize that it will be adequate for anti-viral prophylaxis as intended in this study. The dose will of course be adjusted based on GFR and in pediatric patients based on their weight as detailed in package insert and below.

No major side effects are anticipated since even very high doses of valA (8g/day), for post-KTx CMV prophylaxis were shown to have no severe or treatment-limiting side effects compared to placebo (10).

2 Study Objectives

Primary Objectives:

To compare the effectiveness of valacyclovir (valA) compared valganciclovir (valG) in the prevention of EBV and CMV viremia post-KTx.

To compare the proportion of patients requiring dose reduction or cessation of valA compared to valG due to adverse drug side effects.

Secondary Objective:

To identify the presence and quantity of EBV and CMV in renal tissue biopsies from kidney transplant recipients.

3 Study Design

This is a single-center, prospective, randomized, pilot study of up to 200 kidney transplant recipients from the University of Minnesota Medical Center. Randomization of subjects will be in a 1:1 ratio to receive either ValA or standard of care regimen of ValG. Duration of therapy will be 3-13 months.

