6.2 Treatment Regimen

Dosing of valG and valA will be based on level of renal function assessed by glomerular filtration rate (GFR).

Table 2: valA (valAcyclovir) dosing based on GFR

GFR	> 50ml/min	30-49ml/min	10-29ml/min	< 10ml/min
Adults	1500mg BID	1000mg BID	500mg BID	500mg QD
Children	20mg/kg BID	15mg/kg BID	7.5mg/kg BID	7.5mg/kg QD

Table 3: valG (valGanciclovir) dosing based on GFR

GFR	\geq 60ml/min	40-59ml/min	25-39ml/min	10-24 ml/min	< 10ml/min
Adults	900mg QD	450mg QD	450mg QOD	450 mg twice weekly	Hold dose
Children	7 x BSA x Creatinine Clearance (CrCl) (calculated by modified Schwartz formula and Cockcroft-Gault for less than and equal to 17 years of age respectively; max 900 QD; max CrCl 150 mL/min/1.73 mL/m²)				

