6.4 Method for Assigning Subjects to Treatment Groups

Subjects will be randomized by the IDS pharmacy in 1:1 fashion using computer allocation to receive either ValA or ValG, and will notify the study team of the randomization assignment

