6.5 Preparation and Administration of Study Drug

After randomization, the treating investigator will order the treatment following this protocol dosing schema (see Tables 2 and 3). Commercial supply of ValA and ValG will be dispensed to the subjects.

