6.6 Known Adverse Effects

As extracted from the package inserts for the study drugs, these are the known adverse effects for this protocol.

	Val G	Val A
COMMON Side Effects	headache nausea abdominal pain hematologic toxicity diarrhea fever tremor	headache nausea abdominal pain

	graft rejection vomiting hypertension upper respiratory infection urinary tract infection insomnia	
RARE adverse reactions	acute renal failure allergic reaction bleeding complications nervous system effects: agitation, hallucinations, confusion, delirium, seizures, swelling of the brain general pain, fatigue, weakness, edema abnormal lab results that might indicate abnormal organ function skin rash cough shortness of breath	acute renal failure allergic reaction bleeding complications nervous system effects: agitation, hallucinations, confusion, delirium, seizures, swelling of the brain

6.7 **Subject Compliance Monitoring**

Subjects will be asked to adhere to their prescribed treatment and dosage. Medication adherence will be assessed by the study team during routine visits, by reviewing the medical record, and by communication with the subject or guardian (table in section 5.4).

6.8 **Prior and Concomitant Therapy**

All prior and concomitant therapies will be documented and allowed as per standard of care procedures. Provided there are no direct interactions with the randomized medication, all medications will be prescribed as standard of care. Management of all viral disease is as per physician and will not be protocolled by research procedures.

6.9 **Blinding of Study Drug**

Not applicable.

7 Statistical Plan

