7.1 Primary Study Endpoints

The primary study endpoints are as follows:

1. Incidence and duration of CMV and EBV viremia and magnitude of viremia as measured by area under the viral load-time curve of recipients who become viremic with CMV and/or EBV in the first year post-Ktx.
2. Incidence of subjects developing drug related side effects requiring dose reduction or cessation.
3. Presence of EBV and or CMV in renal tissue (protocol biopsies).

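### Primary endpoint 2 rests on unblinded attribution with no stated criteria, so an arm difference could be created or distorted by how dose changes are labelled

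*Combined protocol and SAP*

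**What the plan says.** Section 7.1 lists three primary endpoints, with no rule for combining them. The second is "Incidence of subjects developing drug related side effects requiring dose reduction or cessation". It serves the second primary objective in section 2: "To compare the proportion of patients requiring dose reduction or cessation of valA compared to valG due to adverse drug side effects".

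On who knows the arm, section 6.9 gives blinding as "Not applicable". Under section 6.4 the pharmacy randomises and "will notify the study team of the randomization assignment". Under section 6.5 "the treating investigator will order the treatment following this protocol dosing schema". Section 1.1 summarises the expected result in advance: "valA is less expensive, with fewer adverse effects, and less likelihood of causing leucopenia than valG".

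On dosing, section 6.2 says "Dosing of valG and valA will be based on level of renal function assessed by glomerular filtration rate (GFR"). The bands in Table 2 (valA) and Table 3 (adult valG) differ, and paediatric valG follows a formula in creatinine clearance. Section 6.6 lists acute renal failure among the rare reactions of both drugs.

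The plan gives no criteria for judging a side effect drug related, no assessment blinded to arm, no statement on whether a GFR-table change counts, and no test for this endpoint. The synopsis names Fisher's exact test for viremia incidence only.

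**The concern.** Two judgements make an event: that the dose had to change, and that the drug was the reason. Both are made by people who know the arm, under a protocol that describes one drug as the less toxic. Section 6.6 also lists more known effects for valG, hematologic toxicity among them, so there are more labels at hand for that arm. If the same clinical picture is called drug related more often in one arm, the endpoint differs between arms with no difference in toxicity.

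The GFR tables add a second, weaker route. When renal function falls, the table changes the dose. Staff can record that as a routine adjustment or as a renal side effect that required a reduction, and nothing in the plan decides which.

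At stake is one of the two primary objectives, and the tolerability half of the case for replacing valG.

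**Working it through.** **1. No figure to reproduce.** The documents give no expected rate, effect size or power for this endpoint. The sample size in section 7.4 concerns CMV viremia and does not bear on it.

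**2. How much attribution imbalance matters.** Inputs from the documents: 200 subjects at 1:1 (sections 3 and 7.4), hence 100 per arm at most, and significance at p ≤ 0.05 (synopsis). Assumptions: Fisher's two-sided test is used here too; the true rate p is equal in both arms; d extra points are attributed in one arm only. Then

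P(significant) = Σₓ Σᵧ Bin(x; 100, p) · Bin(y; 100, p + d) · 1[Fisher p-value for (x, y) ≤ 0.05].

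Exact enumeration gives:

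| True rate in both arms (assumed) | d = 0 | d = 5 | d = 10 | d = 15 |
|---|---|---|---|---|
| 5% | 2.1% | 19.0% | 58.6% | 88.3% |
| 10% | 2.9% | 13.9% | 44.4% | 76.2% |
| 15% | 3.3% | 11.5% | 35.9% | 66.9% |
| 20% | 3.3% | 10.1% | 31.3% | 60.8% |

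The calculation is symmetric: it does not matter which arm receives the extra points. A lower true rate makes the same imbalance more damaging.

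**3. Direction of the GFR route.** Adult cut-points are 50, 30 and 10 for valA (Table 2) and 60, 40, 25 and 10 for valG (Table 3). Reading single falls off the tables:

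- GFR 62 to 55: valG goes from 900 mg QD to 450 mg QD; valA is unchanged.
- GFR 55 to 45: valA goes from 1500 mg BID to 1000 mg BID; valG is unchanged.
- GFR 35 to 28: valA goes from 1000 mg BID to 500 mg BID; valG is unchanged.

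Now assume a uniform starting GFR and a 20% relative fall. From a start of 60–90, valA steps down if 0.8 × GFR < 50, that is below 62.5: 2.5/30 = 8%. ValG steps down if 0.8 × GFR < 60, that is below 75: 15/30 = 50%. From a start of 30–60, valA steps down from 50–60 and from 30–37.5: (10 + 7.5)/30 = 58%. ValG steps down from 40–50 and from 30–31.25: (10 + 1.25)/30 = 38%. The sign reverses. The documents give no GFR distribution, so the net direction is unknown.

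**4. Why a plain all-cause count cannot replace the endpoint.** Section 6.3 lets subjects on valA with CMV disease or repeated viremia stop valA and start valG. No matching rule is written for valG. An all-cause count would record these efficacy failures as valA events. Section 7.4 takes 80% on valA to be free of CMV viremia at 6 months, so up to 100 − 80 = 20 points could arise this way; how many would switch is not known. By the formula in step 2 at a 15% true rate, 5, 10, 15 or 20 extra points in valA alone give significance in 11.5%, 35.9%, 66.9% or 88.5% of trials. That is as large a bias as the one to be removed, against the other arm.

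**The case against.** The strongest reply is that the endpoint is sound as worded. It requires a side effect, judged drug related, that forces the change. A table adjustment is neither, so it counts only if someone miscodes it. That stands: the defect on the GFR side is a missing rule, not a built-in count.

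A reader might infer from the different bands that the endpoint is structurally tilted towards valA. The documents do not support this. The 60 cut-point affects only valG, but the 50 and 30 cut-points affect only valA, and which effect prevails depends on baseline GFR.

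Other features push the opposite way or are neutral. Section 5.3 specifies monthly safety laboratories for valA recipients, while the section 5.4 schedule makes no distinction by arm; if 5.3 were followed, more events could be found on valA. Section 1 notes that leucopenia may be met by reducing MMF, which would keep valG toxicity out of this endpoint.

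It is also fair to say that every rate in the illustration is assumed, that 100 per arm is a ceiling, and that the trial is labelled a pilot. Calling the endpoint co-primary, in the sense that all must succeed, would go beyond the text. None of this supplies attribution criteria, and an open-label design does not prevent adding them.

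**Conclusion.** The concern holds as one of possible bias through unblinded attribution without criteria, in one of three listed primary endpoints. The section 1.1 statement makes attribution against valG the likelier error, but the documents do not show that it would occur or how large it would be. The GFR route is secondary, works only through misclassification, and has no known direction.

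The size is illustrative: with a 15% true rate, 5 to 15 extra points in one arm raise the chance of a false difference from about 3% to between 11% and 67%. This assumes a Fisher test, 100 analysed per arm and no true difference.

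The plan should be changed. The open-label design itself need not be.

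**What to change.** 1. Keep the attributed endpoint, state the attribution criteria and name the test.
2. Add a CRF reason code for every dose change: side effect, GFR-table adjustment, switch for CMV disease or viremia under section 6.3, graft failure, pregnancy, planned completion, other.
3. Add a sensitivity analysis of all reductions or cessations regardless of attribution, excluding planned completion and CMV efficacy switches. Show it with and without GFR-table changes, since some of those may be true nephrotoxicity. Report each excluded category by arm.
4. Add leucopenia/neutropenia by arm from the scheduled CBCs, at a threshold fixed in advance, as the objective supporting analysis. It also captures leucopenia managed by MMF reduction.
5. Reconcile section 5.3 with section 5.4 on safety laboratories, so that events are looked for equally in both arms.

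The cost is SAP wording and one CRF field; the section 5.4 schedule already includes CBCs. The downside is that the sensitivity analysis counts some changes unrelated to drug, which dilutes a true difference. It should therefore be read beside the attributed endpoint and not in its place.

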7.2 Secondary Study Endpoints

Organ donor and recipient demographics, transplant characteristics, donor/recipient infection history (pre-transplant EBV and CMV IgE antibody status and qPCR in donors and recipients.

7.3 Primary Safety Endpoints

Interim analysis will be done after the enrollment and completion of therapy with study drug valA or standard of care drug valG in 6 patients. If there is $\geq 20\%$ increased incidence of CMV / EBV viremia in the valA cohort compared to the valG cohort then study will be stopped.

- Risks related to steroids
- Hypertension
- Cardiovascular disease
- Diabetes
- Malignancy

Adverse Event Reporting Period

The study period during which adverse events must be reported is normally defined as the period from the initiation of any study procedures to the end of the study treatment follow-up. For this study, the study treatment follow-up is defined as 30 days following the last administration of study treatment.

Preexisting Condition

A preexisting condition is one that is present at the start of the study. A preexisting condition will be recorded as an adverse event if the frequency, intensity, or the character of the condition worsens during the study period.

General Physical Examination Findings

At screening, any clinically significant abnormality will be recorded as a preexisting condition. At the end of the study, any new clinically significant findings/abnormalities that meet the definition of an adverse event will also be recorded and documented as an adverse event.

Post-study Adverse Event

All unresolved adverse events will be followed by the investigator until the events are resolved, the subject is lost to follow-up, or the adverse event is otherwise explained. At the last scheduled visit, the investigator will instruct each subject to report any subsequent event(s) that the subject, or the subject's personal physician, believes might reasonably be related to participation in this study.

Abnormal Laboratory Values

A clinical laboratory abnormality should be documented as an adverse event if any one of the following conditions is met:

- The laboratory abnormality is not otherwise refuted by a repeat test to confirm the abnormality
- The abnormality suggests a disease and/or organ toxicity
- The abnormality is of a degree that requires active management; e.g. change of dose, discontinuation of the drug, more frequent follow-up assessments, further diagnostic investigation, etc.

Hospitalization, Prolonged Hospitalization or Surgery

Any adverse event that results in hospitalization or prolonged hospitalization will be documented and reported as a serious adverse event unless specifically instructed otherwise in this protocol. Any condition responsible for surgery should be documented as an adverse event if the condition meets the criteria for an adverse event.

Neither the condition, hospitalization, prolonged hospitalization, nor surgery are reported as an adverse event in the following circumstances:

- Hospitalization or prolonged hospitalization for diagnostic or elective surgical procedures for a preexisting condition. Surgery should **not** be reported as an outcome of an adverse event if the purpose of the surgery was elective or diagnostic and the outcome was uneventful.
- Hospitalization or prolonged hospitalization required to allow efficacy measurement for the study.
- Hospitalization or prolonged hospitalization for therapy of the target disease of the study, unless it is a worsening or increase in frequency of hospital admissions as judged by the clinical investigator.

8.1 Recording of Adverse Events

At each contact with the subject, the investigator must seek information on adverse events by specific questioning and, as appropriate, by examination. Information on all adverse events will be recorded immediately in the source document, and also in the appropriate adverse event module of the case report form (CRF). All clearly related signs, symptoms, and abnormal diagnostic procedures results will be recorded in the source document, though should be grouped under one diagnosis.

All adverse events occurring during the study period must be recorded. The clinical course of each event will be followed until resolution, stabilization, or until it has been determined that the study treatment or participation is not the cause. Serious adverse events that are still ongoing at the end of the study period must be followed up to determine the final outcome. Any serious adverse event that occurs after the study period and is considered to be possibly related to the study treatment or study participation should be recorded and reported immediately.

8.2 Reporting of Serious Adverse Events

8.2.1 Study Sponsor Notification by Investigator

A serious adverse event must be reported to the Principle Investigator within 24 hours of finding out of the event. Within the following 48 hours, further information on the serious adverse event must be documented in the form of a written narrative. This should include a copy of the completed Serious Adverse Event form (see Appendix), and any other diagnostic information that will assist the understanding of the event. Significant new information of ongoing serious adverse events should be provided promptly to the PI. The PI will keep a copy of this SAE form on file at the study site. Report serious adverse events by phone and facsimile to:

[name] [name]
[contact]
[contact]

At the time of the initial report, the following information should be provided:

- Study identifier
- Study Center
- Subject number
- A description of the event
- Date of onset
- Current status
- Whether study treatment was discontinued
- The reason why the event is classified as serious
- Investigator assessment of the association between the event and study treatment

8.2.2 IRB Notification by Investigator

Reports of all serious adverse events (including follow-up information) must be submitted to the IRB within 5 working days if it falls under the expedited reporting

guidelines. Copies of each report and documentation of IRB notification and receipt will be kept in the Clinical Investigator's binder.

8.2.3 FDA Notification by Sponsor

The study sponsor shall notify the FDA by telephone or by facsimile transmission of any unexpected fatal or life-threatening experience associated with the use of the drug as soon as possible but no later than 7 calendar days from the sponsor's original receipt of the information.

If a previous adverse event that was not initially deemed reportable is later found to fit the criteria for reporting, the study sponsor will submit the adverse event in a written report to the FDA as soon as possible, but no later than 15 calendar days from the time the determination is made.

Agency	Criteria for Reporting	Timeframe	Form to Use	Submission address/fax numbers
U of MN IRB	Unanticipated death of a locally enrolled subject(s); New or increased risk; Any adverse event that requires a change to the protocol or consent form- refer to the IRB website for complete details	5 working days	UMN IRB Report Form	email to [contact]
	Other Problems or Events meeting the definition of Prompt Reporting per the IRB's website	5 working days	UMN IRB Report Form	email to [contact]
FDA	SAE: fatal, life-threatening, unexpected, at least possibly related	7 calendar days	FDA MedWatch	– MedWatch Online Voluntary Reporting Form www.accessdata.fda.gov/scripts/medwatch
	SAE: serious, unexpected, at least possibly related	15 calendar days		

